### 4.0 Study Methods

**4.1 Study Overview:** The study design incorporates a 3 year, two-visit longitudinal cohort study of 96 HIV+ subjects who are non-diabetic at enrollment but either at high risk (i.e., pre-diabetic) or lower risk (i.e., not pre-diabetic) of progressing to clinical diabetes, in addition to a cross-sectional study which will compare these non-diabetic HIV+ subjects to an additional 40 HIV+ diabetics and 40 HIV-negative diabetics (see **Figure**). The baseline and follow-up study visits will include fasting peripheral blood collection, glucose tolerance testing, CT quantification of adipose tissue, and subcutaneous abdominal adipose tissue biopsies using a liposuction cannula system to collect approximately 10 ml of tissue.

**4.2 Participant Recruitment:** HIV+ participants will be recruited from the Vanderbilt Comprehensive Care Clinic (VCCC), the largest HIV provider in central Tennessee and a principal study site for the AIDS Clinical Trials Group (ACTG). In 2014, a total of 2,954 HIV+ patients had at least one VCCC visit, including 358 new patients (up from 297 in 2013), and over 250 antiretroviral therapy-naïve adults start treatment yearly. Diabetic patients without HIV will be recruited from the Vanderbilt *ResearchMatch* cohort, an electronic clinical study volunteer registry. In March 2016 there were 180 adult volunteers with Type 2 diabetes mellitus within 50 miles of Vanderbilt University.

#### 4.3 Inclusion Criteria for HIV+ Participants:

- On antiretroviral therapy for at least 18 months
- HIV-1 RNA <50 copies/ml for the prior 12 months
- CD4+ count >350 cells/ $\mu$ l in the prior 12 months
- HbA1c in prior 6 months within specified limits (See Figure)
- Pre-menopausal by self-report
- No known inflammatory or rheumatologic conditions
- No heavy alcohol (>11 drinks per week) or cocaine, amphetamine, or illicit (non-

- prescribed) opiate abuse by self-report
- Not on GLP-1 agonists or DPP-4 inhibitors (diabetic participants only)

[figure not shown]
#### 4.4 Inclusion Criteria for HIV-negative Participants:

- A HbA1c >6.5% or a fasting glucose >126mg/dl, or on anti-diabetic medications for at least 6 months
- Pre-menopausal by self-report
- No known inflammatory or rheumatologic conditions
- No heavy alcohol (>11 drinks per week) or cocaine, amphetamine, or illicit (non-prescribed) opiate abuse by self-report
- Not on a GLP-1 agonist or DPP-4 inhibitor

The fasting glucose, hemoglobin A1c (HbA1c), and/or anti-diabetic medication requirements for inclusion in one of the three HIV+ groups or the one HIV-negative group are shown in the **Figure**. The fasting glucose of 100mg/dl and HbA1c of 5.7% separating the two HIV+ non-diabetic groups are based on American Diabetes Association cutoffs for pre-diabetes.

In selecting HIV+ participants, we will maintain a similar median age in each group, and we will recruit roughly equal numbers of white and non-white participants (reflecting the VCCC demographics), equal men and women, and an equal number of obese and non-obese (BMI >30 kg/m^2) in each group. We will also strive to enroll at least half our participants on an integrase strand transfer inhibitor (INSTI)-based regimen. INSTIs are becoming a preferred antiretroviral agent to the exclusion of some older agents. This strategy will aid in understanding

**Figure: Subject groups, study design, and proposed assays**

Assays performed at each clinical visit :

- Clinical** → Glucose tolerance testing, CT fat quantification
- Adipose tissue** → Extracted T cells:
  - Flow cytometry & FACS sorting
  - CD4+ & CD8+ single T cell RNA expression profiling\*
  - CD4+ digital droplet latent HIV quantification (HIV+ only)
  - CD8+ T cell receptor sequencing\*
- Tissue** : Quantitative mRNA expression (macrophage activation and M1 vs. M2 phenotype cytokines, and adipocyte regulatory proteins)
- Peripheral blood** → T cell flow cytometry, CD4+ digital droplet latent HIV quantification (HIV+ only)

\*Single T cell RNA expression profiling and CD8+ T cell receptor sequencing will only be performed at the baseline visit. Cells will be stored from the follow-up visit.

potential racial, sex, and antiretroviral medication factors in our analysis.

As with the HIV+ subjects, we will aim to recruit roughly equal numbers of white and non-white participants, equal men and women, and an equal number of obese and non-obese HIV-negative subjects.

The enrollment schedule is shown in **Table 4**. We have estimated at least 80% of the HIV+ non-diabetic participants will be retained for the follow-up visit 3 years later ( $\geq 40$  per group) based on loss and refusal rates in VCCC ACTG longitudinal studies. Participants will be actively followed by the research nurse and asked to complete the second visit early if they plan to move out of the area or start on anti-diabetic medication.

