**Table 4. Enrollment by study group and year**

	Year 1				Year 2				Year 3				Year 4				Year 5				Total visits
	Q 1	Q 2	Q 3	Q 4	Q 1	Q 2	Q 3	Q 4	Q 1	Q 2	Q 3	Q 4	Q 1	Q 2	Q 3	Q 4	Q 1	Q 2	Q 3	Q 4	
Clinical visits																					
Baseline visit: HIV+ non-diabetics		10	20	20	20	20	6														96
Baseline visit: HIV+ diabetics							10	10	7	7	6										40
Baseline visit: HIV-negative diabetics									6	7	7	10	10								40
Follow-up visit: HIV+ non-diabetics																20	20	20	20		80

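### Minor: retaining at least 80% of 96 HIV+ non-diabetic participants does not secure at least 40 per group; the smaller group can be counted on for at most 38.4, and 40 per group needs 83.3%

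*Protocol*

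**What the plan says.** Section 4.1 describes a "two-visit longitudinal cohort study of 96 HIV+ subjects who are non-diabetic at enrollment", who are either pre-diabetic or not. Section 4.4 confirms that there are two such groups: it gives the fasting glucose and HbA1c cutoffs "separating the two HIV+ non-diabetic groups". The size of each group does not appear in the readable text; it may be in the Figure, which is not reproduced.

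The paragraph that introduces Table 4 then says: "We have estimated at least 80% of the HIV+ non-diabetic participants will be retained for the follow-up visit 3 years later". A parenthesis in that sentence restates this as 40 or more per group, and the source is given as "based on loss and refusal rates in VCCC ACTG longitudinal studies".

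Table 4 lists 96 baseline visits for these participants. In the row "Follow-up visit: HIV+ non-diabetics" it lists four quarters of 20 visits, 80 in all.

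**The concern.** The sentence gives two lower bounds as if one were the head-count form of the other: a retention rate of at least 80% and a retained size of at least 40 per group. With 96 enrolled, the first does not deliver the second. A cohort could meet the stated retention rate and still miss the stated group size.

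This is the only retained sample size that the protocol gives for its longitudinal part, and Table 4 schedules visits to match it. Anyone who takes 40 per group as the guaranteed minimum for a change-over-time analysis would start from a number that the retention estimate does not support.

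**Working it through.** **Inputs**

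- Enrolled HIV+ non-diabetic participants: 96 (section 4.1). Table 4 agrees: 10 + 20 + 20 + 20 + 20 + 6 = 96.
- Number of groups: 2 (sections 4.1 and 4.4).
- Retention floor: 80% (text introducing Table 4).
- Stated retained size: at least 40 per group, so at least 80 in total (same sentence).
- Planned follow-up visits: 20 + 20 + 20 + 20 = 80 (Table 4).
- Assumption, where a split is needed: 48 per group. This is the most favourable case.

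**Attempt to reproduce the stated figure**

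Retained = enrolled × retention.

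- Total: 96 × 0.80 = 76.8, against 80 stated.
- Per group at 48/48: 48 × 0.80 = 38.4, against 40 stated.

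The stated figure is not reproduced. In whole people, the smallest total that meets the floor is 77 (77/96 = 80.2%), and with 77 people in two groups the smaller has at most 38.

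**Dependence on the split**

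The bound does not rest on equal groups. If 76.8 are retained in total, the smaller retained group cannot exceed 76.8 / 2 = 38.4. Unequal enrolment makes it harder. With 50 and 46 enrolled, 80% of the smaller group is 46 × 0.80 = 36.8, and reaching 40 there needs 40/46 = 87.0%.

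**What 40 per group requires**

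- Retention, with 96 enrolled equally: 40/48 = 80/96 = 83.3%.
- Enrolment, with 80% retained: 40/0.80 = 50 per group, 100 in total.

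**Size of the discrepancy**

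- 80 − 76.8 = 3.2 people in total; 40 − 38.4 = 1.6 per group.
- Ratio of standard errors: √(80/76.8) = 1.021, about 2% wider.

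**Chance of reaching the stated size**

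This treats each return as an independent event with the same probability p and assumes 48 per group. The first result is P(X ≥ 80) for X ~ Binomial(96, p). The second is the square of P(X ≥ 40) for X ~ Binomial(48, p).

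| True retention p | At least 80 of 96 return | Both groups reach 40 |
|---|---|---|
| 80% | 25% | 13% |
| 83.3% | 57% | 35% |
| 85% | 73% | 51% |
| 90% | 99% | 91% |

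At the stated floor the stated size would usually be missed. It becomes reliable only when true retention is close to 90%.

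**The case against.** The strongest reply is that the figures are compatible. Any retention of 83.3% or more satisfies both the 80% floor and 40 per group, and the 80 visits in Table 4 agree exactly with 40 per group. On that reading the planners expected about 83% and wrote it as a round, cautious bound. The protocol also provides active nurse follow-up and an early second visit for participants who plan to move or to start anti-diabetic medication, both of which should help retention. The per-group gap is under two people, and nothing in the readable text is calculated from it.

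Much of this stands. The statements are not mutually exclusive, and true retention may well exceed 80%; the site rates behind the estimate are not shown. The probabilities at exactly 80% describe the floor, not a forecast. The effect is small. Table 4 is a schedule, so its 80 visits are not themselves an error.

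It does not rescue the sentence. Both numbers are given as minimums, with the second as the equivalent of the first. If 77 of 96 return, the first is met and the second must fail. Nor does 38.4 round to 40.

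**Conclusion.** The point holds, at minor severity. The 80% floor supports 76.8 people in total and at most 38.4 in the smaller group; 40 per group needs 83.3% retention. The totals and the 38.4 bound hold for any division of the 96. The 83.3% is the lowest rate that could suffice and rises if the groups are unequal. The probabilities rest further on independent returns at a common rate.

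The consequence is limited to a stated minimum that is about 3 people too high for the retention rate given, with a precision cost of about 2% at the floor. Since no visible power or precision calculation uses it, no design or analysis decision is shown to be affected.

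**What to change.** Correct the retention sentence in one of two ways.

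1. Keep the 80% estimate, restate the minimum retained sample as about 77 in total (about 38 per group), and mark the 80 follow-up visits in Table 4 as a target. Base any longitudinal precision statement on 77.
2. Keep the minimum of 40 per group and state retention as at least 83.3% (80 of 96, with equal groups), if the site loss and refusal rates cited there support it.

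The first is the safer choice unless those rates are clearly above 83.3%. Either is a one-line edit. The first costs a slightly less favourable stated size; neither needs extra participants or a change in design.

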**Table 4. Enrollment by study group and year**

	Year 1				Year 2				Year 3				Year 4				Year 5				Total visits
	Q 1	Q 2	Q 3	Q 4	Q 1	Q 2	Q 3	Q 4	Q 1	Q 2	Q 3	Q 4	Q 1	Q 2	Q 3	Q 4	Q 1	Q 2	Q 3	Q 4	
Clinical visits																					
Baseline visit: HIV+ non-diabetics		10	20	20	20	20	6														96
Baseline visit: HIV+ diabetics							10	10	7	7	6										40
Baseline visit: HIV-negative diabetics									6	7	7	10	10								40
Follow-up visit: HIV+ non-diabetics																20	20	20	20		80

## 4.5 Study Procedures

**Blood collection:** We will collect 80 ml of fasting peripheral blood by percutaneous venipuncture on the left or right upper extremity. We will collect an additional 5 ml of blood at -15, 0, 30, 60, 90, and 120 min after ingestion of the oral glucose tolerance test (the 90 minute collection may be omitted if CT scan is performed during this time).

**Adipose tissue biopsy:** We will collect approximately 10 ml of subcutaneous adipose tissue (equivalent to roughly 9.5 g) using a specialized 2.7 mm blunt, side-ported peripheral liposuction catheter (Tulip CellFriendly™ GEMS system, Tulip Medical Products) designed for the efficient extraction of viable adipocytes and stromal vascular cells for outpatient cosmetic re-injection procedures. The GEMS system is ideal for our study due to the quantity of adipose tissue which can be obtained without injury to the cells. The procedure takes less than 15 minutes and blood loss is generally zero. This liposuction procedure is a standard technique for outpatient collection of subcutaneous adipose tissue and has been performed over 300 times at Vanderbilt.

**Oral glucose tolerance test:** All subjects will be fasting. We will draw blood at -15, 0, 30, 60, 90, and 120 min after oral administration of 75 g glucose syrup for measurement of serum glucose, insulin and C-peptide (the 90 minute collection may be omitted if CT scan is performed during this time). Glucose tolerance will be classified according to current American Diabetes

Association guidelines. Although the primary outcome will be two-hour glucose, we will calculate insulin sensitivity as the homeostasis model assessment (HOMA2) of insulin sensitivity ([www.dru.ox.ac.uk](http://www.dru.ox.ac.uk)). We will also calculate the Matsuda Index as  $10,000/\text{sqrt}(\text{Glucose}_0 \times \text{Insulin}_0 \times \text{mean glucose} \times \text{mean insulin})$  and the Insulinogenic Index defined as  $\Delta\text{Insulin} (0-30, \text{pmol/L})/\Delta\text{Glucose} (0-30, \text{mmol/L})$ .

**CT adipose tissue quantification:** A noninvasive CT scanning protocol will be performed using established methods previously used in NHLBI/NIA cohort studies to measure adipose tissue mass and distribution, including abdominal subcutaneous and visceral fat, liver adiposity, pericardial adiposity, and thigh adipose tissue and muscle. **Appendix 1** describes the scanning protocol.

**Health and behavior assessment:** We will assess diet, activity level, alcohol intake, family history, and health behaviors using a modified version of the Wellspring Health Risk Assessment (see **Appendix 2**). Selected variables will be included in the statistical models if associated with the outcomes.

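### Does the optional 90-minute OGTT draw leave the Matsuda Index without a consistent definition?

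*Protocol*

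**What the plan says.** Protocol section 4.5 sets the sampling schedule: "We will draw blood at -15, 0, 30, 60, 90, and 120 min after oral administration of 75 g glucose syrup". Both the blood collection and the OGTT paragraphs of that section add the allowance that "the 90 minute collection may be omitted if CT scan is performed during this time".

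On outcomes, the OGTT paragraph says "Although the primary outcome will be two-hour glucose", insulin sensitivity will also be derived by HOMA2. It continues, "We will also calculate the Matsuda Index as" 10,000 divided by the square root of fasting glucose × fasting insulin × mean glucose × mean insulin. Two references are attached to the sentence that defines this index and the Insulinogenic Index. The Insulinogenic Index carries its time window (0 to 30 minutes). The Matsuda means carry none.

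OGTT and CT belong to the same visits. Section 4.1 says "The baseline and follow-up study visits will include fasting peripheral blood collection, glucose tolerance testing, CT quantification of adipose tissue", and the Figure lists "Glucose tolerance testing, CT fat quantification" among the assays at each clinical visit. Paired visits are limited to the row "Follow-up visit: HIV+ non-diabetics" of Table 4, with 80 visits planned.

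**The concern.** The protocol fixes a formula that depends on a mean over the OGTT, and separately makes one of the candidate samples optional for a reason unrelated to the participant's metabolism. It does not say which samples enter the mean, whether the mean is arithmetic or time-weighted, or what happens when the 90-minute value is absent. An analyst who averaged whatever was available would use five samples for some visits and four for others (six and five if the -15 minute sample is counted).

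Glucose and insulin at 90 minutes are often still high in people with impaired tolerance, so dropping that sample tends to lower the means and raise the index. CT timing would then contribute to differences between participants and, for those seen twice, to apparent change over three years. If omission were commoner in one group or at one visit, the result would be bias and not just noise. OGTT and CT are both done at all 96 + 40 + 40 + 80 = 256 planned visits, so the overlap could arise at any of them.

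**Working it through.** The protocol states no figure on this point, so there is none to reproduce. The check has two parts.

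**Which quantities use the 90-minute sample**

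| Quantity | Samples needed | Affected? |
|---|---|---|
| Two-hour glucose (primary) | 120 min | No |
| HOMA2 | Fasting | No |
| Insulinogenic Index | 0 and 30 min | No |
| Matsuda Index | Fasting plus the OGTT means | Only if the means include 90 min |

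The omission rule touches only the 90-minute draw. The set 0, 30, 60, 120 is therefore scheduled at every visit.

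**Size of the effect if the means use whatever was drawn**

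The protocol gives no OGTT curves, omission rates or SDs, so all of these are assumptions. Assumed values at 0/30/60/90/120 min (glucose mg/dL; insulin µU/mL):

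- Normal: 90, 140, 125, 110, 100; 7, 55, 55, 45, 35
- Pre-diabetic: 105, 165, 185, 175, 155; 12, 60, 90, 95, 90
- Diabetic: 145, 215, 265, 280, 265; 14, 35, 50, 60, 62
- Fast-return normal: 88, 150, 110, 80, 85; 6, 70, 50, 20, 18

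Worked case, pre-diabetic, arithmetic means, -15 min not counted:

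- With 90 min: mean glucose 785/5 = 157.0, mean insulin 347/5 = 69.4. Index = 10,000/√(105 × 12 × 157.0 × 69.4) = 2.70.
- Without 90 min: 610/4 = 152.5 and 252/4 = 63.0. Index = 10,000/√(105 × 12 × 152.5 × 63.0) = 2.87, a shift of +6.5%.

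Same case, time-weighted (trapezoidal) means, area divided by 120 minutes:

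- With 90 min: 163.75 and 74.0, index 2.56.
- Without 90 min: 162.5 and 72.75, index 2.59, a shift of +1.2%.

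| Curve | Arithmetic | Trapezoidal |
|---|---|---|
| Normal | 5.97 to 6.06 (+1.5%) | 5.54 to 5.53 (-0.3%) |
| Pre-diabetic | 2.70 to 2.87 (+6.5%) | 2.56 to 2.59 (+1.2%) |
| Diabetic | 2.18 to 2.35 (+7.5%) | 2.11 to 2.15 (+1.9%) |
| Fast-return normal | 7.50 to 6.97 (-7.1%) | 6.84 to 6.41 (-6.2%) |

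Counting a -15 min value equal to the 0 min value, the arithmetic shifts are +3.5%, +8.4%, +8.8% and -4.7%. A late-peaking curve (106, 160, 190, 200, 180; 12, 50, 80, 120, 110) gives +11.4% arithmetic and +5.4% trapezoidal. Size and sign therefore depend on the assumed curve.

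*Noise.* If a share p of visits omits the draw, added SD on the log scale = |ln(shift ratio)| × √(p(1 - p)). For the pre-diabetic curve with p = 0.5:

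- Arithmetic: ln(1.065) × 0.5 = 0.0315 (0.0404 with -15 min counted).
- Trapezoidal: ln(1.0124) × 0.5 = 0.0062.

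Against an assumed between-person log SD of 0.5, variance rises by 0.0315²/0.5² = 0.4% (0.7% with -15 min). At a log SD of 0.3 it rises by 1.1% (1.8% with -15 min). With trapezoidal means the rises are 0.0062²/0.5² ≈ 0.02% and 0.0062²/0.3² ≈ 0.04%.

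*Paired visits.* With independent omission at each visit, discordant pairs = 80 × 2p(1 - p), which is about 14, 30 or 40 at p = 10%, 25% or 50%. Each such pair on the pre-diabetic curve carries an artificial change of about 6% to 8% (arithmetic) or 1% (trapezoidal), in either direction.

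*Group gap, normal minus pre-diabetic, -15 min not counted.*

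| | 90 min for all | Only pre-diabetics omit | All use 0/30/60/120 |
|---|---|---|---|
| Arithmetic | 3.27 | 3.10 (-5.4%) | 3.19 (-2.6%) |
| Trapezoidal | 2.98 | 2.95 (-1.1%) | 2.94 (-1.6%) |

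If half of each group omits the draw, the arithmetic gap is the average of the first and third columns, (3.27 + 3.19)/2 = 3.23. That lies between two consistent definitions, either of which would be acceptable.

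**The case for a change.** The strongest argument for a change is that the protocol did not leave this index wholly to the analysis plan. It wrote out the formula, gave the time window for the neighbouring index but not for this one, and introduced the rule that makes one input variable. The references attached to the index sentence cannot be consulted here, and the omission rule is this study's own.

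Table 4 also enrols the groups in sequence. HIV+ non-diabetic baselines come first, then HIV+ diabetics, then HIV-negative diabetics, with follow-up visits from late in Year 4. Any drift in CT scheduling over calendar time would line up with group and visit. One sentence would close the gap at no cost in samples.

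The reading of the text stands: the sample set is not stated. So does the observation that the shift depends on curve shape and need not cancel between groups even when omission is balanced.

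The rest carries less weight. Sequential enrolment is a route by which differential omission could arise, not evidence that it does. Choosing time points, an averaging method and a rule for an absent sample is derived-variable detail that commonly sits in an analysis plan, and that document is not at hand. A fixed four-point set is also not clearly the best definition. With trapezoidal means it moves the group gap more (-1.6%) than the extreme case it would guard against (-1.1%). With arithmetic means it does better than that case (-2.6% against -5.4%). A time-weighted mean with a rule for a missing 90-minute value is an equally defensible choice.

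Whether the -15 minute sample counts is a separate matter. Adding it raises the five-point arithmetic index by 8.9% to 10.8% on all four tabulated curves, so it affects level far more than contrasts within the study.

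**Conclusion.** No change to the protocol is needed. The text is silent on which samples form the Matsuda means, but it states nothing wrong and contradicts nothing. The formula and the sampling allowance are compatible, and a uniform 0/30/60/120 reading fits the wording. Because those four samples are never optional, an analyst can apply one definition to every participant and visit, and the dependence on CT timing then disappears.

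Even if the means were taken over whatever was drawn, the consequence would be confined to one additional index. On the assumed pre-diabetic curve with half of visits omitting the draw, variance rises by 0.4% to 1.8% with arithmetic means and by 0.04% or less with trapezoidal means. Shifts for a single participant can reach several percent, up to about 11% on a late-peaking curve. Bias from CT timing would require omission to differ by group or visit, which the protocol does not show.

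These sizes rest entirely on assumed curves, omission rates and between-person SDs, and indicate order of magnitude only. That two-hour glucose, HOMA2 and the Insulinogenic Index are unaffected rests on no assumption, since none of them uses the 90-minute value.

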## 5.0 Risks to Study Participants

**5.1. Potential Risks:** The procedures presenting potential risks of this clinical study include phlebotomy, percutaneous adipose tissue biopsy, radiographic imaging, oral glucose tolerance testing, pregnancy testing and a breach of confidential information. Common risks of phlebotomy include pain, local skin irritation, and formation of a superficial hematoma; more severe risks would include local or systemic infection or accidental cannulation of an artery (all uncommon).

Risks from the adipose tissue biopsy include pain, local skin irritation, bruising, bleeding, and formation of a hematoma in the subcutaneous tissue; more severe risks would include local or systemic infection, or difficult to control bleeding (all uncommon). Lidocaine may cause local discomfort during injection or a rash, redness or soreness at the injection site, and in rare cases could induce a transient alteration in heart rhythm (suction is applied to the syringe prior to injection to ensure the lidocaine is not being injected into a vessel).

The risks of the oral glucose tolerance test include nausea or vomiting following ingestion of the 75 g glucose solution.

The CT scan will include imaging of the abdomen, the thigh, and the chest (pericardial fat). The average amount of radiation a person will receive from the CT scan is estimated to be 7 mSv (range 3.5 -14 mSv), or 14 mSv for those patients seen at both the baseline and follow-up visits (separated by more than 3 years). This can be compared to the radiation people in the U.S. receive every year from natural sources (about 3 mSv). By contrast, people who work with radiation have a yearly exposure limit of 50 mSv. Therefore, the estimated total radiation exposure at the initial and follow-up visits will be approximately equal to slightly more than four years of background radiation from natural sources.

All female patients will receive a pregnancy test, and a negative test result will be a prerequisite for any further study procedures. The major risk of the pregnancy test is disclosure of a previously unknown pregnancy.

To reduce the risk of potential disclosure of identifying information, study participants will be

assigned a study number (not derived from any personal information) to identify all samples and study records, and the key linking study numbers to medical record numbers will be maintained in a locked file in the locked, private office of the PI. We believe this system will provide a high degree of security to maintain the confidentiality of personal health information.

**5.2. Biohazard Risks:** Participants in this study will not be treated with any biological agents or administered any substances that could present a biohazard risk (aside from lidocaine). However, the serum samples, adipose tissue biopsies, and mononuclear cells collected from participants in this study represent biohazardous specimens and will be handled according to biohazard protocols in place at Vanderbilt University. Since each participant will undergo study procedures individually, study volunteers are not expected to be at risk of exposure to biological samples from other participants at any time. Samples will be collected by trained research staff and needles and other equipment will be disposed of in the appropriate containers for processing by the Medical Center waste facility.

**5.3. Protections against Risk:** The planned study procedures are all commonly used in immunologic and metabolic clinical research and will be performed by personnel with specialized training. The VCCC ACTG research facility has a long history of successful participation in complex multi-center clinical studies and a competent, professional research staff. To reduce the risk of loss of confidentiality, each study participant will be assigned a unique study ID number that is not derived from any personal identifier. All participant computer data entry forms, imaging results, and samples will be labeled with this unique study number; no specimens or data forms will include any personal identifiers. Only the PI will have access to the key linking the study ID to a VUMC medical record number, and this information will be maintained in a locked filing cabinet in the locked office of the PI (who will be responsible for maintaining the confidentiality of this document). All study data will be collected and stored in the REDCap database, a centralized, password protected electronic research database created and maintained by the Vanderbilt Institute for Clinical and Translational Research. Data collection at the time of the visit will be computer-based to the extent feasible, reducing the need for paper data reports or forms. The electronic data will be uploaded to REDCap. The only patient identifiers included in the REDCap database (as defined by HIPPA) will be dates (month/date/year) related to clinical care (e.g., date of treatment start). Only the PI and the project biostatisticians ([name] PhD and [name] MS) will have access to the REDCap study database.

**5.4. Potential Benefits of the Research:** While the proposed research will not have direct benefits to the study participants, the risks of the study are reasonable in relation to the benefit to HIV-infected adults as a population. The study findings will be directly relevant to the design of intervention trials to reduce metabolic disease risk in HIV-infected adults, which could lead to changes in clinical practice that benefit study participants in the future.

